Test product: BI 1467335 film-coated tablets				
dose: 3, 6 and 10 mg qd (Japanese) and 10 mg qd (Caucasian)				
mode of admin.: Oral administration with 240 mL water after an overnight fast of at least 10 hours				
Comparator product: Placebo				
dose: Not applicable (matching placebo tablets)				
mode of admin.: Oral administration with 240 mL water after an overnight fast of at least 10 hours				
Duration of treatment: 28 days with multiple oral doses of BI 1467335 q.d.				

Proprietary confidential information © 2017 Boehringer Ingelheim International GmbH or one or more of its affiliated companies

Name of company: Boehringer Ingelheim		Tabulated Trial Protocol		
Name of finished product: Not applicable				
Name of active ingredient: BI 1467335				
Protocol date: 11 May 2017	Trial number: 1386-0007		Revision date: Not Applicable	
Criteria for pharmacokinetics: Secondary endpoints: After the first dose: AUC ₀₋₂₄ and C _{max} of BI 1467335 After the last dose: AUC _{0-24,28} and C _{max,28} of BI 1467335				
Criteria for pharmacodynamics:				
Criteria for safety: Primary endpoint: The number [N (%)] of subjects with drug-related AEs				
Statistical methods: Descriptive statistics will be calculated for all endpoints. Dose proportionality of BI 1467335 will be explored using a regression model; a 95% confidence interval for the slope will be computed.				

Proprietary confidential information © 2017 Boehringer Ingelheim International GmbH or one or more of its affiliated companies

FLOW CHART

Visit	Day	Planned time (relative to first drug administration [h:min])	Approximate clock time of actual day [h:min]	Event and comment	Safety laboratory	PK blood ⁹			12-lead ECG ⁸	Vital signs (BP, PR)	Questioning for AEs and concomitant therapy ⁶
1	-28 to -2			Screening (SCR) ^{1, 5, 12}	x ⁵				x	x	
2	-3 to -1 ⁷	-48:00	09:00	Ambulatory visit	x				x	x	x
	-1	-12:00	21:00	Admission to trial site	x ⁵						x
1	1	-2:00	07:00	Allocation to treatment ²	x ^{2,13}			x ^{2, 16}	x ²	x ²	x ²
		-0:05	08:55			x ¹⁴	x ¹⁰				
		0:00	09:00	First drug administration			▲				
		0:15	09:15		x			x			
		0:30	09:30		x			x	x		
		0:45	09:45		x			x	x		
		1:00	10:00		x			x	x	x	
		1:30	10:30		x			x			
		2:00	11:00	240 mL fluid intake and light breakfast ³	x			x	x	x	
		3:00	12:00		x						
		4:00	13:00	240 mL fluid intake, thereafter lunch ³	x	+		x	x	x	
		6:00	15:00		x						
		8:00	17:00	Snack (voluntary) ³	x	+		x	x	x	
		10:00	19:00	Dinner ³	x						
		12:00	21:00		x	+		x	x	x	

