3.3.4 Removal of subjects from therapy or assessments

3.3.4.1 Removal of individual subjects

An individual subject is to be removed from the trial if:

1. The subject withdraws consent, without the need to justify the decision
2. The subject needs to take concomitant drugs that interfere with the investigational product or other trial medication
3. The subject is no longer able to participate for other medical reasons (such as surgery, adverse events, or diseases)
4. An AE or clinically significant laboratory change or abnormality occurred that the investigator judges to warrant discontinuation of treatment. This may include cases of sustained symptomatic hypotension (BP <90/50 mmHg) or hypertension (BP >180/100 mmHg) or of clinically relevant changes in ECG requiring intervention as well as unexplained liver enzyme elevations at any time during the trial.

In addition to these criteria, the physician may discontinue subjects at any time based on his or her clinical judgment.

A subject can also be removed from the trial if eligibility criteria are being violated or if the subject fails to comply with the protocol (for instance, by non-adherence to dietary rules, or non-attendance at study assessments).

Proprietary confidential information © 2017 Boehringer Ingelheim International GmbH or one or more of its affiliated companies

If a subject is removed from or withdraws from the trial prior to first administration of trial medication, the data of this subject will not be entered in the case report form (CRF) or trial database and will not be reported in the clinical trial report (CTR). The only exception to this rule is when the subject had an AESI and/or SAE that the investigator considers related to the screening procedure. If a subject is removed from or withdraws from the trial after first administration of trial medication, this will be documented and the reason for discontinuation must be recorded in the CRF. In this case, the data will be included in the CRF/trial database and will be reported in the CTR. At the time of discontinuation a complete EOT examination will be performed if possible and the information will be recorded in the CRFs. These discontinuations will be discussed in the CTR.

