6. INVESTIGATIONAL PLAN

6.1 VISIT SCHEDULE

All visits must be performed as specified in Flow Chart. The investigator/sponsor can decide to perform an unscheduled visit if deemed necessary for any valid reasons.

Further details of measurement performed during the study are specified under [Section 5](#).

Time windows are permitted as follows:

- General medical examination: at screening (1 to 21 days prior to Day1) and at the end-of-trial evaluation (within 14 to 20 days after last drug administration).
- BP and PR: ± 15 min (0:30, 0:45, 1:00, 2:00) and ± 30 min (4:00, 8:00, 12:00) on Day 1, Day 14 and Day 28, ± 60 min on other days and up to 3 hours prior to drug administration if indicated "before drug administration"
- ECG: ± 15 min (0:15, 0:30, 0:45, 1:00, 1:30, 2:00) and ± 30 min (4:00, 8:00, 12:00) on Day 1, Day 14 and Day 28, ± 60 min on other days.
ECGs on Day 1, 2, 14, 15, 28 and 29: for the second and third ECG a time interval of 1-3 min between ECGs should be maintained
- Laboratory/urinalysis: Up to 3 hours prior to drug administration if indicated "before drug administration". Urinalysis test can be done up to 3 hours prior to drug administration at some other time points indicated in the flow chart.
- Pharmacokinetic blood sampling for predose concentration in multiple dose part: ± 5 min (has to be done before drug administration)

Other pharmacokinetic blood sampling / urine collection: For planned individual plasma concentration sampling times refer to Flow Chart. While these nominal times should be adhered to as closely as possible, the actual sampling times will be recorded and used for the calculation of pharmacokinetic parameters.

The designation "before" on Day 1 refers to the time period of 3 hours before drug administration (see [Flow Chart](#)), i.e., study measurements and assessments scheduled to occur "before" have to be performed and completed within 3 hours prior to drug administration.

Relevant time violations will be identified and their handling discussed no later than at the (B)RPM.

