6.2.3 End of trial and follow-up period

For AE assessment, laboratory tests, recording of ECG, vital signs and body weight, and physical examination during the EOT period, see [Sections 5.2.2 to 5.2.5](#).

Subjects who discontinue treatment before the end of the planned treatment period should undergo the EOT visit.

All abnormal values (including laboratory parameters) that are judged clinically relevant by the investigator will be monitored using the appropriate tests until a return to a medically acceptable level is achieved. All (S)AEs, including those persisting after individual subject's end of trial must be followed up until they have resolved, have been sufficiently characterized, or no further information can be obtained.

In the case of a subject's discontinuation from the trial, the subject will be followed-up until the investigator or sub-investigator is convinced of the subject's safety. When follow-up is not possible or comes to an end, it should be formally completed after discussion with the sponsor. If a subject stops attending trial assessments, the investigator should assess the subject's status as comprehensively as possible and the well-being of the subject should be monitored. However, if the subject withdraws from the trial, it is the subject's choice whether or not to participate; he or she cannot be compelled.

The end of the trial as a whole is defined by the 'last regular visit completed by last subject' or 'end date of the last open AE' or 'date of the last follow-up test' or 'date of an AE has been decided as sufficiently followed-up', whichever is latest.

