### **5.4.3 Treatment compliance and treatment exposure**

Treatment compliance will be based on data from the subject diary. The subjects will report whether they took study medication during the treatment period. For each subject, percent compliance will be calculated as the number of times they reported taking study medication (i. e. number of non-missing actual administration date on CRF) divided by the number of tablets which should have been taken was given times 100. If subjects discontinued study, denominator is defined as the number of the dates from day 1 to day of discontinuation.

Treatment exposure is defined as the number of days taking medication and the total dose of BI 1467335 per subject.

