## **7.3 TREATMENT COMPLIANCE**

Treatment compliance (%) will be analysed using descriptive statistics and also using frequency tables for categories of treatment compliance. Categories will be defined as <80%, 80% - 100% and >100%.

Any deviations from complete intake will be addressed in the RPM/DBLM (cf. [Section 6.2](#)) and described in the CTR.

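### For subjects who leave the study, the compliance denominator counts days on which no dose was due, so a subject who took every dose due can be classed below 80%

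*SAP*

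**What the plan says.** SAP 5.4.3 takes as numerator the "number of times they reported taking study medication", counted as non-missing administration dates on the CRF. For subjects who stay in the study this is "divided by the number of tablets which should have been taken was given times 100". For those who leave, the rule changes: "If subjects discontinued study, denominator is defined as the number of the dates from day 1 to day of discontinuation".

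SAP 7.3 summarises the percentage and tabulates it in classes: "Categories will be defined as <80%, 80% - 100% and >100" per cent.

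The dosing period is shorter than the study. The Protocol synopsis gives "Duration of treatment: 28 days with multiple oral doses of BI 1467335 q.d". The Flow Chart then has ambulatory visits on Days 30, 32, 36 and 40 and an end-of-trial examination on Day 42 to 48, which matches the 14 to 20 days after the last dose in Protocol 6.1.

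Two Protocol passages bear on early stopping. Section 6.2.3 says: "Subjects who discontinue treatment before the end of the planned treatment period should undergo the EOT visit". Section 3.3.4.1 says: "At the time of discontinuation a complete EOT examination will be performed if possible".

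**The concern.** The numerator can grow only on days when a dose is taken. The denominator for leavers grows on every calendar day up to study exit. The two can part in three ways:

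- **(a)** All 28 doses taken, then withdrawal during the drug-free follow-up.
- **(b)** Treatment stopped early, with study exit recorded some days later.
- **(c)** Exit in the morning, before that day's dose.

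In each case the subject may have taken every dose due, and the percentage still drops. In (a), a subject with identical dosing who completes follow-up is judged against what was due, so the same adherence gives two different results. The below-80% class could then combine subjects who skipped home doses with subjects who skipped none. Groups are small: Protocol Table 3.1: 1 has 9 active subjects per group, so one misclassed subject is 1/9 = 11.1% of an arm. In the Caucasian placebo group of 3 it is 1/3 = 33.3%.

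**Working it through.** The plan states no compliance figure to reproduce, so the check applies the definition directly.

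**Inputs**
- Numerator: dosing occasions reported (SAP 5.4.3).
- Denominator for leavers, as written: D, the number of dates from Day 1 to study discontinuation (SAP 5.4.3).
- Dosing: once daily, Days 1 to 28 (Protocol synopsis).
- End of trial: 28 + 14 = Day 42 to 28 + 20 = Day 48 (Flow Chart; Protocol 6.1).
- Class boundary: below 80% (SAP 7.3).
- Assumption: a completer's denominator is meant as 28 dosing occasions, giving 28/28 = 100%.

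**(a) All 28 doses taken, exit on Day D in follow-up.** Compliance = 28/D, which is below 80% when D > 28/0.80 = 35.

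| Exit day | Compliance | Class |
|---|---|---|
| 30 | 28/30 = 93.3% | 80–100% |
| 35 | 28/35 = 80.0% | 80–100% |
| 36 | 28/36 = 77.8% | below 80% |
| 40 | 28/40 = 70.0% | below 80% |
| 48 | 28/48 = 58.3% | below 80% |

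Day 48 is the outer edge of the end-of-trial window.

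**(b) Every dose taken to last dose day L, exit recorded on Day D.** Compliance = L/D, which is below 80% when D > 1.25 × L. The values of L are illustrative.
- L = 7: from Day 9, 7/9 = 77.8%, a gap of 2 days.
- L = 14: from Day 18, 14/18 = 77.8%, a gap of 4 days.
- L = 21: from Day 27, 21/27 = 77.8%, a gap of 6 days.
- Outer case: L = 10 with exit 14 to 20 days later gives 10/24 = 41.7% to 10/30 = 33.3%.

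**(c) Exit before the dose on Day d, all previous doses taken.** Compliance = (d − 1)/d.
- Day 2: 1/2 = 50%. Day 3: 2/3 = 66.7%. Day 4: 3/4 = 75%. All are below 80%.
- Day 5: 4/5 = 80.0%, so the class is no longer affected.

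**With the denominator limited to doses due.** (a) 28/28 = 100%. (b) with L = 10 and the stop documented before the Day 11 dose: 10/10 = 100%. (c) on Day 4: 3/3 = 100%. A subject who silently stops home dosing after Day 10 and whose treatment is documented as discontinued before the dose on Day 21 still scores 10/20 = 50.0%.

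**The case against.** **The sentence may be meant for treatment days only.** SAP 5.4.3 opens by referring to medication taken during the treatment period, and the leaver rule reads naturally as a way to shorten the denominator. If the programmer takes the day of discontinuation as the last treatment day, (a) disappears and (b) largely does. That is a fair account of the probable intent. But the sentence is triggered by leaving the study, and nothing in either document supplies the treatment-day reading. Two programmers could derive different values.

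**Early stoppers should leave promptly.** Protocol 3.3.4.1 asks for the end-of-trial examination at discontinuation where possible, and lists an adverse event warranting the end of treatment as a reason for removal from the trial. This stands as a limit on (b): the 33% to 42% figures are a worst case, and the documents do not say how often a long gap would occur. It does not help (a) or (c).

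**The affected windows are narrow.** This also stands. Case (a) changes the class only from Day 36, and (c) only on Days 2 to 4, before which dosing was supervised in-house.

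**Other displays show what happened.** SAP 7.7 tabulates days on medication and lists every administration; disposition is reported; SAP 7.3 sends departures from complete intake to the report planning meeting. A careful reader could trace each case. That limits the harm but does not make the percentage right.

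**Counting to study exit charges silent non-adherence.** A subject who quietly stops home dosing should not score 100%, and a denominator cut at the last dose taken would allow that. The objection is sound and shapes the fix.

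**Conclusion.** The rule, read as written, gives a wrong number for some subjects who missed nothing. The firmest case is full dosing followed by withdrawal on Day 36 or later: 77.8% falling to 58.3%, against 100% for a completer with the same intake. Exit before the dose on Days 2 to 4 gives 50% to 75%. Delayed recording of exit after an early stop may do the same, by an amount the documents do not fix.

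This is a minor point. It rests on the literal wording of SAP 5.4.3 and on completers being judged against 28 occasions.

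A reader might infer more than the documents support:
- *That safety or PK results are affected.* Adverse events are analysed on the treated set and PK on the PK parameter set, and neither uses the compliance percentage (SAP 6.3). A subject in (b) or (c) stopped before Day 28 and would have no Day 28 profile to interpret.
- *That the error will follow one arm.* No discontinuation rate is given, so any imbalance is conjecture.
- *That values near 33% to 42% are typical.* They need a 14 to 20 day gap that Protocol 3.3.4.1 is meant to avoid.

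**What to change.** Replace the leaver sentence in SAP 5.4.3 with:

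> For subjects who discontinue, the denominator is the number of scheduled dosing days from Day 1 to the earlier of Day 28 and the documented date on which treatment was permanently discontinued (by decision of the investigator, sponsor or subject), excluding that date if discontinuation preceded the scheduled dose. Doses missed before that documented date remain in the denominator.

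The last sentence keeps silent non-adherence visible. Early stopping itself is already shown in the disposition and days-on-medication tables and needs no new display.

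The cost is one sentence and one derivation line. Administration dates are on the CRF. The documents do not name a CRF field for the date of permanent treatment discontinuation, so the programmer should confirm where it is recorded, and whether it can be placed before or after that day's dose. No dose, visit or clinical rule changes.

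The preceding sentence should be clarified in the same edit. Its denominator is in tablets while the numerator counts dosing occasions; that is a separate matter, and nothing above depends on it.

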## **6. GENERAL ANALYSIS DEFINITIONS**

### **6.1 TREATMENTS**

For basic study information on treatments to be administered, assignments of dose groups, and selection of doses, cf. Section 4 of the CTP.

Subjects were treated with 3 mg, 6 mg or 10 mg of BI 1467335 (test treatment, T) or placebo (reference treatment, R) once daily over 28 days. Three placebo groups will be defined: Placebo for Japanese, Placebo for Caucasians and Total placebo. Placebo for Japanese will be defined as a pooled group of the Japanese subjects receiving placebo treatment in the three dose groups. Placebo for Caucasians will be defined as the placebo subjects in the 10 mg dose group for Caucasians (which comprises all placebo-treated Caucasian subjects). Total placebo will be defined as one pooled placebo group (i.e. no distinction between dose groups and ethnicity will be made for placebo subjects).

For statistical analysis of AEs, safety laboratory data, vital signs and ECG, the following analysis phases are defined for each subject:

Table 6.1: 1 Flow chart of analysis phases for statistical analyses of AEs, safety laboratory data, vital signs and ECG

| Study analysis phase | Label  | Start (inclusive)                               | End (exclusive)                                    |
|----------------------|--|---|--|
| Screening            | Screening  | Date of informed consent                        | Date/time of first administration of study drug    |
| On-treatment         | Placebo,
3 mg BI for
Japanese,
6 mg BI for
Japanese,
10 mg BI for
Japanese
or 10 mg BI for
Caucasians,
respectively | Date/time of first administration of study drug | 0:00 on day after subject's trial termination date |

CTR Section 15, Appendix 16.1.9.2.8.2 and Appendix 16.1.9.2.8.3 AE displays will present results for the on-treatment phase only.

In CTR Section 15 AE tables (but not in Appendix 16.1.9.2.8.2 and Appendix 16.1.9.2.8.3 AE tables), the following totals will be provided in addition:

- "**Total BI**", defined as the total over all on-treatment phases involving BI, i.e., "3 mg BI for Japanese" + "6 mg BI for Japanese" + "10 mg BI for Japanese" + "10 mg BI for Caucasians"
- "**Total BI for Japanese**", defined as the total over all on-treatment phases involving BI, i.e., "3 mg BI for Japanese" + "6 mg BI for Japanese" + "10 mg BI for Japanese"
- "**Total on-trt**", defined as the total over all on-treatment phases, i.e., "Placebo" + "3 mg BI for Japanese" + "6 mg BI for Japanese" + "10 mg BI for Japanese" + "10 mg BI for Caucasians"

CTR Appendix 16.1.9.2.8.1 displays will present results for the screening and on-treatment phases.

Additionally to the totals defined above, the following total will be provided in CTR Section 16.1.9.2.8.1 AE tables:

- "**Total**", defined as the total over all study phases (screening + on-treatment)

More details on the technical implementation of these analyses are provided in the ADS Plan of this TSAP.

## **6.2      IMPORTANT PROTOCOL VIOLATIONS**

Data discrepancies and deviations from the CTP will be identified for all subjects in the database (i.e., treated subjects). Consistency check listings (for identification of violations of time windows) and a list of protocol deviations (e.g. deviations in drug administration, in blood sampling times, etc.) will be provided to be discussed at the RPM/DBLM. At this meeting, it will be decided whether a discrepant data value can be used in analyses or whether it must be corrected in the clinical database. Each protocol deviation must be assessed to determine whether it is an IPV. For definition of IPVs, and for the process of identification of these, refer to the BI reference document "Protocol Violation Handling Definitions" ([1](#)).

If any IPVs are identified, they are to be summarised into categories and will be captured in the RPM/DBLM minutes via an accompanying Excel spreadsheet ([2](#)). The following table contains the categories which are considered to be IPVs in this trial. If the data show other IPVs, this table will be supplemented accordingly by the time of the RPM/DBLM.

IPVs will be summarised and listed.

Table 6.2: 1      Important protocol violations

| Categor y/Code | Description                                      |   | Example/Comment   |
|----------------|--|---|---|
| A       | Entrance criteria not met                 |   |   |
|                | A1   | Inclusion criteria not met  | Inclusion criteria not met as specified in the protocol   |
|                | A2   | Exclusion criteria met  | Exclusion criteria met as specified in the protocol   |
| B       | Informed consent                          |   |   |
|                | B1   | Informed consent not available/not done                                   | Informed consent date missing   |
|                | B2   | Informed consent too late   | Informed consent date was after screening visit   |
| C       | Trial medication and randomization        |   |   |
|                | C1   | Incorrect trial medication taken  | The contents of medication kit do not match with the randomisation  |
|                | C2   | Randomisation order not followed  | Subject received trial medication from medication kit assigned to another subject   |
|                | C3   | Non-compliance  | Medication not taken as scheduled by protocol   |
|                | C4   | Medication code broken inappropriately                                    | Medication code was broken with no valid reason   |
| D       | Concomitant medication                    |   |   |
|                | D1   | Any prohibited concomitant medications/therapies use                      | Intake of medications/therapies that might reasonably influence the results of the trial  |
| E       | Missing data                              |   |   |
|                | E1   | Certain violations of procedures used to measure secondary PK endpoint    | 
Violations of PK sampling which may cause no secondary PK endpoint.
 
Handling for violation relating PD sampling will be discussed on RPM.
 |
| F       | Incorrect timing                          |   |   |
|                | F1   | Certain violations of time schedule used to measure secondary PK endpoint | 
PK sample taken too early/too late
 
Handling for violation relating PD sampling will be discussed on RPM.
                      |
| G       | Other trial specific important violations |   |   |
|                | G1   | Incorrect intake of food  | The subject who eats food within 10 hours before the medication intake on the visit days  |

 Time deviations will only be flagged as iPV, when one of the secondary endpoint of the subject cannot be evaluated

